Booster 50 µg	Participants randomized in the blinded phase and received booster 50 µg in Part C Date of reference: date of booster	From dose date in Part C to earlier date of (DBL or data cutoff date for safety, last observed in study ^a).
Not received booster	Participants randomized to/received mRNA-1273 in Part A or B and did not receive booster in Part C Date of reference: date of BD-visit 1	Up to earlier date of (DBL or data cutoff date for safety, last observed in study ^a).
Placebo	Participants randomized to/only received Placebo in Part A or B and did not receive booster in Part C Date of reference: date of BD-visit 1	From BD-visit 1 in Part C to earlier date of (DBL or data cutoff date for safety, last observed in study ^a).
Effectiveness, Immunogenicity of mRNA-1273 primary Series		
mRNA-1273	Participants randomized to mRNA-1273 in the Blinded Phase	From Dose 1 of mRNA-1273 to earlier date of (booster date, DBL or data cutoff date, last observed in study ^a).
Placebo-mRNA-1273	Participants randomized to Placebo and received mRNA-1273 in Part B	
Safety of mRNA-1273 primary Series		
mRNA-1273	Participants received mRNA-1273 in the Blinded Phase	From Dose 1 of mRNA-1273 to earlier date of (booster date, DBL or data cutoff date, last observed in study ^a).
Placebo-mRNA-1273	Participants received Placebo in the Blinded phase and received mRNA-1273 in Part B	

^a last observed in study is the earliest date of study discontinuation, study completion, or death.

All analyses will be conducted using SAS Version 9.4 or higher unless otherwise specified.

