5.3.1.2.1. Effectiveness of the primary series

Effectiveness of the primary series of mRNA-1273 in those vaccinated participants, will be assessed in participants initially randomized to the mRNA-1273 group (mRNA-1273, vaccinated from July-December 2020, early vaccinated) and those initially randomized to the placebo group (Placebo-mRNA-1273, vaccinated December 2020-April 2021, recent vaccinated) using the PP Primary Series Set. Part A and Part B data after Dose 1 of mRNA-1273 will be included for this analysis, and date of Dose 1 of mRNA-1273 will be used as the reference. The analysis period will be from Dose 1 of mRNA-1273 to earlier of last study participation, booster date, or data cutoff date for efficacy as presented in Table 1.

Using PP Primary Series Set, participants at risk will be those who did not have evidence of prior infection prior to Dose 1 of mRNA-1273, specifically, those in mRNA-1273 (randomized to mRNA-1273 in Part A (baseline/pre-Day 1 SARS-CoV-2 negative is required for inclusion in PP Primary Series Set), and those in Placebo-mRNA-1273 group who were SARS-CoV-2 negative at PDV/unblinding at the start of Part B.

Incidence rates will be provided over the time from Dose 1 of mRNA-1273 to receipt of booster, last study participation, or data cutoff date for efficacy. Incidence rates will also be provided by calendar quarters, as well as by the following time intervals:

- After Dose 1
 - After Dose 1 of mRNA-1273
 - After Dose 1 to before Dose 2 of mRNA-1273
 - After Dose 2 of mRNA-1273
 - Dose 2 to <14 days after Dose 2
 - ≥ 14 days after Dose 2

The last time interval “ ≥ 14 days after Dose 2” of mRNA-1273 may be further partitioned into shorter intervals. For each interval, person-time is calculated for participants at risk at

the beginning of the interval, as the time from the date of the beginning of the time interval to the date of the event/censoring for subjects with an event/censor if the event/censor occurs in the interval; or the time of the interval for subjects who continue to be at risk at the end of the interval. Incidence rate, and 95% CI for incidence rate will be calculated using the exact method adjusting for person-time will be provided by treatment cohort. Number and incidence rates of COVID-19 starting 14 days after Dose 2 of mRNA-1273 will also be provided by calendar quarters.

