5.4. Safety Analysis

Safety will be assessed by clinical review of all relevant parameters including unsolicited AEs, SAEs, MAAEs, AEs leading to withdrawal from study vaccine and/or study participation, vital signs, and physical examination findings.

Safety analysis of Part B will be based on the Safety Set. Part C safety analyses will be based on the Part C Safety Set. Safety analysis of mRNA-1273 primary series will be based on the Primary Series Safety Set. Analysis period is defined in Section 5.1. All safety analyses will be provided by treatment cohort, unless otherwise specified.

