5.4.1. Unsolicited Treatment-emergent Adverse Events

A treatment-emergent AE (TEAE) is defined as any event occurring during the study not present before exposure to the IP or any event already present that worsens after exposure

to study vaccine. Worsening of a pre-existing condition after vaccination will be reported as a new AE.

Adverse events will also be evaluated by the investigator for the coexistence of MAAE which is defined as an AE that leads to an unscheduled visit to a healthcare practitioner.

Unsolicited AEs will be coded by PT and SOC using MedDRA and summarized by vaccination group.

All summary tables (except for the overall summary of AEs) for unsolicited AEs will be presented by SOC and PT or by PT only for TEAEs with counts of subjects included. SOC will be displayed in internationally agreed order.

When summarizing the number and percentage of subjects with an event, subjects with multiple occurrences of the same AE or a continuing AE will be counted once. Only the maximum severity level will be presented in the severity summaries, and the strongest relationship level will be presented in the relationship summaries. Percentages will be based upon the number of subjects in the Safety Set within each treatment cohort.

Unsolicited TEAEs will be summarized for Part B, Part C, and Primary Series using analysis periods as defined in Section 5.1.

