5.4.1.2. TEAEs by System Organ Class and Preferred Term

The following summary tables of TEAEs will be provided by SOC and PT using frequency counts and percentages (i.e. number and percentage of subjects with an event):

- All unsolicited TEAEs
- All unsolicited TEAEs that are treatment-related
- All serious AEs
- All serious AEs that are treatment-related
- All unsolicited TEAEs leading to discontinuation from study vaccine (mRNA-1273 primary series only)
- All unsolicited TEAEs leading to discontinuation from participation in the study
- All unsolicited severe TEAEs
- All unsolicited severe TEAEs that are treatment-related
- All unsolicited AEs that are medically-attended

Summary tables of all unsolicited TEAEs, Serious AEs, treatment-related SAEs, MAAEs, and TEAE leading to discontinuation from participation in the study will also be provided by SOC and PT.

In addition, summary tables of select TEAEs of clinical interests identified by SMQ will be provided by PT.

Summary of AE of special interest per investigator's assessment will also be provided by SOC and PT.

5.4.1.3.Subgroup Analysis of TEAEs

An overview of TEAE, TEAE summaries presented by SOC and PT will be provided for the following subgroups:

- Age group (<65, and ≥ 65 years)
- Sex (male, female)
- Pre-booster SARS-CoV-2 status
- Race
- Ethnicity

These summaries may be provided for subgroups of select baseline characteristics.

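### Primary-series SAEs, MAAEs, deaths and study discontinuations are shown by cohort as crude percentages over windows about 4.5 months longer in the early-vaccinated cohort than in the crossover cohort

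*SAP*

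**What the plan says.** The Part B/C SAP defines the safety period for the primary series in Table 1 of 5.1.5: "From Dose 1 of mRNA-1273 to earlier date of (booster date, DBL or data cutoff date, last observed in study". The start is each participant's own first mRNA-1273 dose, and no fixed length is set. Section 5.4.1 applies that period to the tables: "Unsolicited TEAEs will be summarized for Part B, Part C, and Primary Series using analysis periods as defined in Section 5.1".

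The measure is a crude percentage. Section 5.4.1 states that "Percentages will be based upon the number of subjects in the Safety Set within each treatment cohort", and 5.4.1.2 has the tables produced "using frequency counts and percentages (i.e. number and percentage of subjects with an event". Section 5.4 adds the layout: "All safety analyses will be provided by treatment cohort, unless otherwise specified". For the primary series, 5.1.4 names two groups, mRNA-1273 and Placebo-mRNA-1273.

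Section 5.3.1.2.1 dates the two cohorts: mRNA-1273 was "vaccinated from July-December 2020, early vaccinated" and Placebo-mRNA-1273 was "vaccinated December 2020-April 2021, recent vaccinated". Crossing over does not restart the study clock: 3.5.1 of the same SAP and 4.1.2 of the protocol end follow-up 24 months after the second dose of the original assignment.

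For effectiveness of the primary series, Table 1 uses the same window wording, but 5.3.1.2 and 5.3.1.2.1 analyse it with person-time, exact confidence intervals, time intervals and calendar quarters.

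**The concern.** A longer window collects more events at the same risk. SAEs, MAAEs and AEs leading to withdrawal are collected throughout Part B (Part A SAP, 6.6.1.6), so the early cohort's extra months do add events to its column.

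The two cohorts stand side by side, and the SAP contrasts the same two cohorts formally for effectiveness (5.3.1.2.1.1), so readers will compare the safety columns too. Equal risk would look like a worse profile in the early cohort, and a real excess among crossovers could be masked.

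The sponsor has met this problem elsewhere. The Part A SAP (6.8.1) notes that burden-of-disease proportions are hard to compare across different follow-up periods and adds a model for that reason. For randomized arms followed concurrently, its 6.1 made up to 28 days after any vaccination the primary safety period. The Part B/C SAP gives no such window for two cohorts that were not vaccinated concurrently.

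**Working it through.** The documents give no expected count or power for primary-series safety, so there is no planned figure to reproduce.

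**Inputs**
- Early cohort Dose 1: July to December 2020 (5.3.1.2.1), mid-point 30 Sep 2020.
- Crossover Dose 1: December 2020 to April 2021 (5.3.1.2.1), mid-point 14 Feb 2021.
- Gap: 137 days; 137 / 30.4375 = 4.5 months. Using mid-points assumes uniform accrual.
- End dates: the SAP's earliest booster interval starts on 1 Sep 2021 (5.3.1.2.2), its data cutoff is April 2022 (5.3.1.2.1), and the last visit is Day 759. Booster dates of 1 Oct and 31 Dec 2021 are assumptions.
- Event rates are assumptions: 2 per 100 person-years for a rare event (SAE), 30 for a common one (MAAE).

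**Formula.** At a constant rate r and follow-up t in years, crude percentage = 1 − exp(−r·t). For rare events the ratio between cohorts tends to the ratio of follow-up times.

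**Same calendar end in both cohorts**

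| End | Follow-up, days (early vs crossover) | Follow-up ratio | At 2/100 PY | At 30/100 PY |
|---|---|---|---|---|
| 1 Oct 2021 | 366 vs 229 | 1.60 | 2.0% vs 1.2% (1.59) | 26.0% vs 17.1% (1.51) |
| 31 Dec 2021 | 457 vs 320 | 1.43 | 2.5% vs 1.7% (1.42) | 31.3% vs 23.1% (1.35) |
| 30 Apr 2022 | 577 vs 440 | 1.31 | 3.1% vs 2.4% (1.31) | 37.7% vs 30.3% (1.24) |
| Day 759 | 758 vs 621 | 1.22 | 4.1% vs 3.3% (1.22) | 46.3% vs 40.0% (1.16) |

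At 60 per 100 person-years the ratio falls to 1.44 at 1 Oct 2021 and 1.11 at Day 759.

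**Crossovers boosted later.** With the early cohort ending on 15 Oct 2021 (380 days), a crossover end of 15 Nov 2021 gives 380 / 274 = 1.39, and 31 Dec 2021 gives 380 / 320 = 1.19.

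**Earlier centre for the early cohort.** The Part A SAP (6.4.2.1) reports a median follow-up of 49 days at the 7 Nov 2020 cutoff. If that is counted from Dose 2 (an assumption), Dose 1 centres on about 22 Aug 2020. The ratio at 1 Oct 2021 is then 405 / 229 = 1.77.

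**After correction.** At an equal constant rate, events per person-year give a ratio of 1.0. A window of 28 days after each of two doses gives 1 − exp(−0.02 × 56 / 365.25) = 0.31% in both cohorts. That window is feasible: a crossover first dosed on 30 Apr 2021 and given Dose 2 at the end of its visit window (28 + 14 days later, 11 Jun 2021) completes it by about 9 Jul 2021, before the earliest booster interval.

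**The case against.** The strongest reply is that these are descriptive tables. Sections 5.4 to 5.4.1.2 plan no ratio, interval or test between cohorts for safety. The AE rate ratio in 6.6.1 of the Part A SAP belongs to Part A. That stands: a reader might infer that the plan would yield a falsely significant safety difference, and the documents do not support this.

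Two other inferences also fail. No pooled primary-series column is planned: 5.1.4 names two groups, and its overall group is for Part C. The 137-day gap does not carry over to the Part B tables, which start at the decision visit, unblinding or first Part B dose (Table 1).

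The size is also uncertain. Booster timing by cohort is not given, and later boosting of crossovers narrows the ratio, in the same direction.

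Person-time is not a complete remedy. If events cluster soon after dosing, crude percentages are nearly right, and open-window rates would reverse the bias: at 1 Oct 2021 the early cohort would show 229 / 366 = 0.63 times the crossover rate at identical risk. Confirmed COVID-19 is recorded as an MAAE (protocol 8.1.2) and varies with calendar time. Crossovers are self-selected and open-label. These points argue for adding a short fixed window and a split of MAAEs, rather than replacing percentages with rates.

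Finally, 5.2.5 plans a summary of time from primary series to booster. This helps for boosted participants, but it is not clearly by cohort and gives no primary-series follow-up time for the never-boosted. Crude percentages do follow protocol 9.5.2.1.

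**Conclusion.** The concern holds for the primary-series tables of SAEs, MAAEs, deaths and AEs leading to study discontinuation. At equal constant risk the early cohort's percentage exceeds the crossover cohort's by about 1.2 to 1.6-fold for rare events with a common calendar end, about 1.2 to 1.4-fold if crossovers are boosted 1 to 2.5 months later, and about 1.1 to 1.5-fold for common MAAEs. The figures rest on uniform accrual within the stated vaccination periods, assumed booster dates and a constant event rate. The direction follows from the plan: the crossover cohort starts later and its clock is not extended.

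The consequence is a display that invites a wrong comparison; no planned test is affected. It is a modest defect that is cheap to correct.

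**What to change.** For the primary series only, keep the counts and percentages in 5.4.1 to 5.4.1.2 and add:

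- For SAEs, MAAEs, deaths and AEs leading to study discontinuation: participants with a first event per 100 person-years with an exact Poisson 95% CI, and total follow-up time by cohort, including never-boosted participants.
- For the same event types: by-cohort percentages within a fixed post-dose window that essentially everyone in both cohorts completes before any booster, for example up to 28 days after any dose, as in 6.1 of the Part A SAP. This covers events that cluster soon after dosing.
- A footnote that the open-window percentages are not comparable between cohorts.
- MAAEs shown with and without confirmed COVID-19.

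Leave AEs leading to discontinuation from study vaccine as a percentage, because in a two-dose series they can arise only before the second dose.

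The cost is SAP wording and slightly larger tables. The dates needed are already collected, and study conduct does not change.

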5.2. Background Characteristics

5.2.1. Subject Disposition

The number and percentage of subjects (analysis sets defined in Section 5) will be summarized by treatment cohort.

The number and percentage of subjects in each of the following disposition categories will be summarized for Part B:

- Received each dose of IP in the blinded phase
- Unblinded in the open-label phase
- Received each dose of mRNA-1273 in the open-label phase
- Prematurely discontinued study IP and the reason for discontinuation
- Prematurely discontinued the study and the reason for discontinuation

The number and percentage of subjects in each of the following disposition categories will be summarized for Part C based on the Part C Safety Set:

- Received booster dose in the BD phase
- Completed study
- Prematurely discontinued the study and the reason for discontinuation

5.2.2. Demographics and Baseline Characteristics

Descriptive statistics will be calculated for the following continuous demographic and baseline characteristics: age (years), weight (kg), height (cm), body mass index (BMI) (kg/m^2). The number and percentage of subjects will be provided for categorical variables such as age group, sex, race, ethnicity, randomization stratum under which the subject was randomized, and risk factors at Screening (have at least one of the following):

- Chronic lung disease (e.g., emphysema and chronic bronchitis, idiopathic pulmonary fibrosis, and cystic fibrosis) or moderate to severe asthma
- Significant cardiac disease (e.g., heart failure, coronary artery disease, congenital heart disease, cardiomyopathies, and pulmonary hypertension)
- Severe obesity (body mass index ≥ 40 kg/m²)
- Diabetes (Type 1, Type 2 or gestational)
- Liver disease
- Human Immunodeficiency Virus (HIV) infection

The summaries will be provided by treatment cohort for Safety Set and Part C Safety Set.

5.2.3. Medical History

Medical history data will be coded by system organ class (SOC) and preferred term (PT) using the Medical Dictionary for Regulatory Activities (MedDRA).

The number and percentage of participants with any medical history will be summarized by SOC, PT, and treatment. A participant will be counted only once for multiple events within each SOC and PT. SOC will be displayed in internationally agreed order.

5.2.4. Prior and Concomitant Medications

Prior and concomitant medications and non-study vaccinations will be coded using the WHO drug dictionary (WHODD). The summary of concomitant medications will be based on the Safety Set. Categorization of prior, concomitant, and post medications for Part B and Part C is summarized in [Appendix C](#).

Concomitant Medications for Part C will be summarized in Part C Safety Set.

5.2.5. Study Exposure

For Part B, the number and percentage of subjects receiving 1st and 2nd dose of mRNA-1273 in Part B, the timing of the 2nd dose will be summarized by treatment cohort for Part B using the Safety Set.

For Part C, the number and percentage of subjects receiving booster dose will be summarized by treatment cohort for Part C using Part C Safety Set.

The summary of time between the 2 doses of primary series, time between the primary series and booster dose, and follow up time after booster dose will be provided.

5.2.6. Major Protocol Deviations

Major protocol deviations are a subset of protocol deviations that may significantly impact the completeness, accuracy, or reliability of the study data or that may significantly affect a subject's rights, safety, or well-being. Major protocol deviations rules will be developed and finalized before database lock.

The number and percentage of the subjects with each major protocol deviation type in Part B and Part C will be provided.

Select major protocol deviations impact critical or key study data, and subjects with such deviations will be excluded from the Per-Protocol sets as defined in Section 5 of this SAP. Such major protocol deviations will be determined and documented by Sponsor prior to DBL. Reasons of exclusion from Per-Protocol Set for efficacy will be summarized.

5.3. Effectiveness Analysis

For Part B, PP Set is the primary analysis population for Part B analysis of effectiveness.

For Part C, the Part C PP Set is the primary analysis population for Part C analysis of vaccine effectiveness, unless otherwise specified. Participants will be included in the treatment cohort for effectiveness analysis as specified in Section 5.1.

Surveillance for COVID-19 will be performed starting after enrollment through the end of the study.

An Adjudication Committee (AC) will review potential cases and adjudicate COVID-19 and severe COVID-19.

5.3.1. Analysis of the Primary Efficacy Endpoint for Part B, Part C, and Long-term Analyses

5.3.1.1. Primary Efficacy Endpoint Definition/Derivation

Vaccine efficacy has been demonstrated based on the primary efficacy endpoint in the blinded phase (Part A) of first occurrence of COVID-19 starting 14 days after the 2nd injection in the blinded phase (Part A).

Part B and Part C are open-label and participants are offered an opportunity to receive the primary series and booster of mRNA-1273 respectively.

Throughout the study, COVID-19 is assessed in the same way as the primary efficacy endpoint in the blinded phase (Part A). An independent external Adjudication Committee (AC) have been adjudicating potential COVID-19 and severe COVID-19 cases. COVID-19 based on AC assessments will be used as the primary approach for COVID-19 throughout the study. COVID-19 cases based on the protocol definition requiring at least 2 eligible systemic symptoms or 1 respiratory symptom after the primary series, and after the booster will also be evaluated.

Derivation of COVID-19 cases based on RT-PCR test results and symptoms is the same as COVID-19 cases for the primary efficacy endpoint as specified in Section 8.1 of the protocol and Section 6.3.1.1 of SAP Version 2.0.

In the Par B open-label phase of the study, all participants will have a scheduled NP swab test and blood collected for immunologic analysis at the PDV. Participants who received mRNA-1273 in the open-label phase will have an additional blood sample collected at OL Day 29 or OL Day 57, depending on the planned number of mRNA-1273 doses to be received in the OL phase. For Part B analysis and analysis of the primary series, subjects with early infection, as detected by positive RT-PCR at scheduled visits (including Day 29 and PDV), or positive bAb against SARS-CoV-2 nucleocapsid protein at scheduled visits,

will be censored at the time of early infection. If a participant had eligible symptom(s) within 14 days of positive RT-PCR at scheduled visits, the participant is considered to be a case for COVID-19.

In the Part C booster dose phase of the study, all participants will have scheduled blood sample collected at BD Day 1 visit. NP swab test at this visit is optional. Participants who received the booster dose of mRNA-1273 in Part C will have blood sample collected at BD Day 29 and BD Day 181 (6 months post-booster). For Part C, subjects with early infection, as detected by positive RT-PCR at scheduled visits, or positive bAb against SARS-CoV-2 nucleocapsid protein at the scheduled visits, will be censored at the time of early infection. If a participant had eligible symptom(s) within 14 days of positive RT-PCR at scheduled visits, the participant is considered to be a case for COVID-19.

Subjects who have no documented COVID-19 will be censored at the earlier date of DBL or data cutoff date for efficacy, date of last observed in study defined as the earlier of study completion date, early discontinuation date from study, or date of death. For analysis of Part B or primary series, subjects who have no documented COVID-19 will be censored at the earlier date of date of booster, DBL or data cutoff date for efficacy, or date of last observed in study defined as the earlier of study completion date, early discontinuation date from study, or date of death.

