7.4. Lost to Follow-up

Participants will be considered LTFU if they repeatedly fail to return for scheduled visits without stating an intention to withdraw consent and they cannot be contacted by the study site. The following actions must be taken if a participant fails to return to the clinic for a required study visit:

- The site must attempt to contact the participant and reschedule the missed visit as soon as possible, counsel the participant on the importance of maintaining the assigned visit schedule, and ascertain whether the participant wishes to and/or should continue in the study.

- Before a participant is deemed LTFU, the investigator or designee must make every effort to regain contact with the participant (where possible, 3 telephone calls and, if necessary, a certified letter to the participant's last known mailing address or local equivalent methods). These contact attempts (eg, dates of telephone calls and registered letters) should be documented in the participant's medical record. A participant should not be considered LTFU until these efforts have been made.
- Should the participant continue to be unreachable, he/she will be considered to have withdrawn from the study.

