For the primary analysis, subjects who have no documented COVID-19 will be censored at the last study assessment date. Subjects who discontinue the study early or die due to causes unrelated to COVID-19 without documented COVID-19 will be censored at the date of early discontinuation or death. Subjects who experience an early COVID-19 up to 14 days after the second injection of IP will be censored at the time of documented COVID-19.

As in PP Set definition, subjects who missed study IP administration, who were seropositive at baseline, or who had major protocol deviations that impact critical or key data, will be excluded from the PP Set.

The number and percentage of subjects who had an event (i.e. the first occurrence of COVID-19 at least 14 days after the second injection) will be reported.

Potential intercurrent events to the estimand are listed in Appendix F Table 9. The primary estimand with rationale for strategies to address intercurrent events is summarized in Appendix F 10.

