Incidence rate will also be provided for the periods defined by emergence and circulation of select variant of interest, e.g. December 2021- data cutoff date (Apr, 2022).

Effectiveness in Part B will be performed, and PP Set will be used with treatment cohorts listed in Table 1 for Part B analysis with similar analysis approach. For Part B, participants at risk at the start of Part B are defined as participants who did not have COVID-19 or SARS-CoV-2 infection and non-positive SARS-CoV-2 status at unblinding/PDV prior to Part B.

5.3.1.2.1.1. Relative Effectiveness of recent vaccinated vs early vaccinated (the Primary Series of mRNA-1273)

Relative effectiveness of recent vaccinated participants (Placebo-mRNA-1273) vs. early vaccinated participants (mRNA-1273) will be assessed using the reduction in incidence rate, calculated as 1- incidence rate ratio (IRR). The 95% CI of reduction in IR will be calculated using the exact method (Poisson distribution) adjusting for person-time.

The above analysis may be performed by calendar quarters and/or time periods.

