5.3.2.1.4. Derivation of asymptomatic SARS-CoV-2 infection

Asymptomatic SARS-CoV-2 infection is identified by absence of symptoms and infections as detected by seroconversion or positive RT-PCR at scheduled visits applicable to individual treatment cohorts for Part B, Part C, and analysis of primary series with corresponding analysis periods:

- Absent of symptoms (no COVID-19 symptom for either efficacy endpoint of COVID-19, or secondary definition of COVID-19),
- AND at least one from below:

- Post-baseline positive RT-PCR at scheduled visits, or
- Seroconversion (bAb specific to SARS-CoV-2 nucleocapsid) at scheduled visits (PDV, OL Day 29, and OL Day 57 in Part B; BD Day 1, BD Day 29, and BD Day 181 in Part C), when blood samples for immunogenicity are collected.

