5.3.2.2. Analysis of Other Efficacy Endpoints

Similar analysis methods as for the endpoint of COVID-19 cases (Section 5.3.1) will be applied to the following efficacy endpoints for analysis of primary series based on the PP set, and for Part C based on the Part C PP Set, unless otherwise specified. Start date to define cases will be similar with that for the endpoint of COVID-19 cases.

- Severe COVID-19
- SARS-CoV-2 infection or COVID-19 regardless of symptomatology or severity
- Asymptomatic SARS-CoV-2 Infection
- COVID-19 using a secondary definition of symptoms
- Death caused by COVID-19

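### After the booster, asymptomatic-infection follow-up runs to data cutoff rather than to the last sample able to detect infection, so interim rates are understated

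*SAP*

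**What the plan says.** All section numbers are from the SAP for Part B and Part C unless stated otherwise.

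- **Censoring rule (5.3.1.1).** "Subjects who have no documented COVID-19 will be censored at the earlier date of DBL or data cutoff date for efficacy", or, if earlier, at the "date of last observed in study defined as the earlier of study completion date, early discontinuation date from study, or date of death". For Part B and primary-series analyses the booster date is added. Table 1, footnote a, repeats the definition: "last observed in study is the earliest date of study discontinuation, study completion, or death". No assessment or sample date enters the rule.
- **Person-time (5.3.1.2.1).** A participant still at risk at the end of an interval contributes the whole interval.
- **Reach (5.3.2.2).** "Similar analysis methods as for the endpoint of COVID-19 cases (Section 5.3.1) will be applied to the following efficacy endpoints", and asymptomatic SARS-CoV-2 infection is on the list. No separate censoring rule is given for it.
- **Detection (5.3.2.1.4).** Asymptomatic infection needs a positive RT-PCR at a scheduled visit, or "Seroconversion (bAb specific to SARS-CoV-2 nucleocapsid) at scheduled visits (PDV, OL Day 29, and OL Day 57 in Part B; BD Day 1", followed by BD Day 29 and BD Day 181. The only scheduled swab in Part C, at BD Day 1, is optional (5.3.1.1).
- **Cutoff.** Section 5.3.1.2.1 gives, as an example of a variant period, "December 2021- data cutoff date (Apr, 2022". Section 5.3.1.2.2 reports post-booster rates for 1 December 2021 to data cutoff.

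**The concern.** Weekly symptom surveillance cannot find an infection without symptoms. Once a participant has given the last nucleocapsid sample before cutoff, no asymptomatic event can be recorded, yet the stated rule keeps adding days to the denominator. The absolute post-booster rate of asymptomatic infection is therefore too low, and the shortfall depends on when people were boosted relative to cutoff.

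The Part A SAP saw the same difficulty in its burden-of-infection analysis (6.8.2). There it limited the summary to sampling periods and to subjects with serology for the period. The Part B and Part C SAP has no such safeguard for this endpoint.

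**Working it through.** **Plan's own figure.** The documents give no person-time, rate or power for Part B or Part C effectiveness. Their one design figure, 151 cases for Part A, reproduces (148.5 fixed-design events × 1.0146 group-sequential inflation = 150.7), but this point does not touch it.

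**One participant.** Take a booster on 31 October 2021. BD Day 29 is 28 November 2021. BD Day 181 is 29 April 2022, or 15 April at the early end of its ±14-day window. With a 1 April 2022 cutoff, this person adds 121 days from 1 December (31 + 31 + 28 + 31) with no listed Part C sample able to show an event. The Day 759 draw does not help: first doses began in July 2020 (5.3.1.2.1), so it falls in late July 2022 or later.

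**Average over participants.**

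Inputs from the documents: counting starts 14 days after the booster (5.3.1.2.2); draws are 28 and 180 days after it (Protocol 4.1.3). Cutoff is April 2022 with no day given, so 1 and 30 April are both shown.

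Assumptions: uniform booster dates, draws on target day, no other draw after BD Day 29, constant hazard. Booster windows are assumed. The 20 September 2021 start matches the eligibility date in the protocol's amendment history.

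- Let p be the share boosted at least 180 days before cutoff, that is by 3 October 2021 (1 April cutoff) or 1 November 2021 (30 April cutoff).
- Counted days = mean days from booster to cutoff − 14.
- Covered days = (28 − 14) + p × (180 − 28) = 14 + 152p.
- Reported rate ÷ rate in covered time = covered ÷ counted.

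Base case, boosters 20 September to 31 December 2021 (103 dates, mean 10 November):

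- 1 April: counted 142 − 14 = 128; p = 14/103 = 0.136; covered 14 + 152 × 0.136 = 34.7; ratio 0.27; uncovered 73%.
- 30 April: counted 157; p = 43/103 = 0.417; covered 77.5; ratio 0.49; uncovered 51%.

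| Booster dates (assumed) | Cutoff | Counted days | Covered days | Uncovered | Ratio |
|---|---|---|---|---|---|
| 20 Sep–30 Nov 2021 | 1 Apr | 144 | 44 | 69.6% | 0.30 |
| 20 Sep–30 Nov 2021 | 30 Apr | 172 | 105 | 39.3% | 0.61 |
| 20 Sep–31 Dec 2021 | 1 Apr | 128 | 35 | 72.9% | 0.27 |
| 20 Sep–31 Dec 2021 | 30 Apr | 157 | 77 | 50.7% | 0.49 |
| 1 Oct 2021–31 Jan 2022 | 1 Apr | 107 | 18 | 83.5% | 0.165 |
| 1 Oct 2021–31 Jan 2022 | 30 Apr | 136 | 54 | 60.6% | 0.39 |
| 20 Sep 2021–1 Mar 2022 | 1 Apr | 98 | 27 | 72.4% | 0.28 |
| 20 Sep 2021–1 Mar 2022 | 30 Apr | 127 | 54 | 57.4% | 0.43 |

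Moving the BD Day 181 draw 14 days either way widens the uncovered range to 29% to 90%.

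**Infection regardless of symptoms.** RT-PCR positives at illness visits still count after the last draw (5.3.2.1.3). If a share s of infections is found only by serology and a share u of time is uncovered, the reported rate is multiplied by 1 − s × u. With assumed s of 0.2 to 0.6 and u of 0.4 to 0.8, the factor runs from 1 − 0.6 × 0.8 = 0.52 to 1 − 0.2 × 0.4 = 0.92.

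**Symptomatic COVID-19, for comparison.** Excess person-time is about λ × g, with λ = −ln(0.98)/365 per day from the 2% annual dropout in Protocol 9.3, and g the gap between last contact and formal withdrawal. For assumed gaps of 14 and 90 days this is 0.08% and 0.5%.

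**The case against.** The strongest reply is that the rule was written for COVID-19, where it works, and that the serology problem is temporary and confined to a descriptive endpoint. Much of that stands.

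- **Completers at final lock.** Their last visit is Day 759 or BD-3, whichever is later (Protocol 4.4), and both include a blood draw, so most of the gap closes. It remains for participants who discontinue or miss draws.
- **The cutoff is an example.** April 2022 appears only as an illustration in the primary-series section. The booster section names no date.
- **Parallel draws.** The original schedule continues, and some Day 394 draws may follow BD Day 29. A first dose on 31 December 2020, the end of the early cohort's stated period, puts Day 394 at 28 January 2022, or 11 February with the 14-day window. For that cohort such a draw shortens the gap but still leaves at least 49 days before 1 April 2022. How many participants it would help is unknown.
- **Status.** Post-booster asymptomatic infection is one of the other efficacy endpoints, with no hypothesis test. The formal Part C comparisons are immunogenicity (Protocol 9.5.3.2).

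A reader might also infer that the COVID-19 rates, or the boosted-versus-unboosted reduction in incidence, are materially biased by silent drop-out. The documents do not support that. Surveillance is weekly, missed eDiary prompts lead to staff contact (Protocol 8.1.2 and 8.2.2), and a participant who cannot be reached does not stay at risk indefinitely: "Should the participant continue to be unreachable, he/she will be considered to have withdrawn from the study". The booster-only safety calls are just three, at BD Day 8, 15 and 22. Unboosted participants keep BD-2, BD-3, the regular calls and the eDiary.

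Nor is the contrast with Part A as sharp as it may look. Its SAP says that "subjects who have no documented COVID-19 will be censored at the last study assessment date", but it also censors early discontinuation and death at those dates, and its analysis period also ends at data cutoff.

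**Conclusion.** The point holds for asymptomatic infection at an interim cutoff, and for participants who discontinue or miss draws. Under the stated rule the absolute post-booster rate is understated. With an April 2022 cutoff and on-time draws, about 39% to 84% of counted time is uncovered (51% to 73% in the base case), and the reported rate is about 0.16 to 0.61 of the rate in covered time. These sizes rest on assumed booster dates, constant hazard and no intervening draw. The direction does not depend on the assumed booster dates.

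Three stronger conclusions do not follow:

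- Infection regardless of symptoms is not understated to the same degree, because symptom-prompted RT-PCR positives are still captured.
- A rate ratio is not biased unless coverage differs between the groups compared.
- Intervals that are too narrow are not a separate harm. An exact Poisson interval scales with person-time, so its relative width depends on the event count; it is misplaced for the same reason as the rate.

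The censoring of symptomatic COVID-19 can stay as it is.

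**What to change.** - **Asymptomatic infection.** In sections 5.3.2.1.4 and 5.3.2.2 and in Table 1 of the SAP for Part B and Part C, censor event-free participants at their last valid nucleocapsid result, or scheduled RT-PCR result, on or before the cutoff, booster (where the analysis ends there) or discontinuation.
- **Infection regardless of symptoms.** Keep the current analysis. Add a sensitivity analysis that censors the whole endpoint at the last valid nucleocapsid result, and state that this drops later PCR-confirmed cases. Do not censor the seroconversion component alone: the composite has a single at-risk clock, so that would be undefined.
- **COVID-19.** No change.

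The cost is SAP wording and programming. Sample dates are already recorded in the eCRF (Protocol 8.1.5). The downside is less person-time and wider intervals for the asymptomatic endpoint.
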